APPENDIX D. LIST OF CONCOMITANT MEDICATIONS REQUIRING CAREFUL MONITORING

CYP Enzymes	Sensitive Substrates	Substrates with Narrow Therapeutic Range
CYP3A	Alfentanil, aprepitant, budesonide, buspirone, conivaptan, darifenacin, darunavir, dasatinib, dronedarone, eletriptan, eplerenone, everolimus, felodipine, indinavir, fluticasone, lopinavir, lovastatin, lurasidone, maraviroc, midazolam, nisoldipine, quetiapine, saquinavir, sildenafil, simvastatin, sirolimus, tolvaptan, tipranavir, triazolam, vardenafil	Alfentanil, astemizole, cisapride, cyclosporine, dihydroergotamine, ergotamine, fentanyl, pimozide, quinidine, sirolimus, tacrolimus, terfenadine

Ref: FDA drug development resources:

(<http://www.fda.gov/drugs/developmentapprovalprocess/developmentresources/druginteractionslabeling/ucm093664.htm#classSub>).

APPENDIX E. ADJUSTED IDEAL BODY WEIGHT (AIBW) CALCULATION

Adjusted Ideal Body Weight (AIBW)

$$\text{AIBW} = \text{IBW}^1 + 0.4 (\text{Actual weight} - \text{IBW}^1)$$

Ideal Body Weight (IBW)

$$\text{IBW}^1 (\text{female}) = 0.9\text{H}^1 - 92$$

(¹H=height in cm; W=weight in kg)

1. INTRODUCTION

1.1. Background

This Statistical Analysis Plan (SAP) is based on Amendment 2 of Protocol IMGN853-0417, dated 28August2020.

A brief history of protocol amendments is presented in Table 1.

Table 1:History of Protocol Amendments

Version Approval Date		Salient Changes (if any) [*]		
Original Protocol	23October2019	N/A		
Amendment 1	18December2019	Increased sample size from 91 to 105		
Amendment 2	28August2020	N/A		

*Changes expected to require accommodation in analysis plan.

This SAP will govern the analysis of study data. The plan for the primary efficacy analysis and all other analyses may be modified prior to final database lock. Any deviations from the SAP will be documented as such in the study report.

2. STUDY DESIGN

2.1. **Protocol Objectives**

2.1.1. Primary Objective

• To determine the efficacy of mirvetuximab soravtansine (MIRV) in patients with platinum resistant ovarian cancer (PROC) and high folate receptor-α (FRα) expression.

2.1.2. Secondary Objectives

2.1.2.1. Key Secondary Objectives:

• To determine the durability of response to MIRV in patients with PROC and high FR α expression.

2.1.2.2. Additional Secondary Objectives:

- To evaluate the safety and tolerability of MIRV.
- To further characterize the clinical activity of MIRV in patients with PROC and high FRα expression.

2.1.2.3. Exploratory Objectives

2.1.3. Study Endpoints

2.1.3.1. Primary Endpoint

• Objective response rate (ORR): includes best response of complete response (CR) or partial response (PR) as assessed by the Investigator.

2.1.3.2. Key Secondary Endpoint

• Duration of response (DOR), defined as the time from initial Investigator-assessed response (CR or PR) until PD as assessed by the Investigator.

2.1.3.2.1. Additional Secondary Endpoints:

- Treatment-emergent adverse events (TEAEs) and laboratory test results, physical examination, or vital signs.
- CA-125 response determined using the GCIG criteria defined in Protocol IMGN853-0417, Appendix C. CA-125 response per GCIG criteria will be determined programmatically.
- Progression-free survival (PFS): defined as the time from first dose of MIRV until Investigator-assessed radiological PD or death, whichever occurs first.
- Overall survival (OS), defined as the time from first dose of MIRV until the date of death. Patients alive at the time of analysis will be censored at the last date known to be alive.
- ORR, DOR, and PFS by blinded independent central review (BICR) will be summarized as sensitivity analysis.

2.1.3.3. Exploratory Endpoints

2.2. Study Overview

This study is designed to evaluate the efficacy and safety of MIRV in women with PROC and high $FR\alpha$ expression.

Eligible patients will receive MIRV 6 mg/kg AIBW Q3W until disease progression, unacceptable toxicity, withdrawal of consent, death, or until the Sponsor terminates the study (whichever comes first).

Tumor assessments, including radiological assessments by CT/MRI scans will be performed at Screening and subsequently every $6 (\pm 1)$ weeks from C1D1 for the first 36 weeks then every 12 (± 3) weeks until disease progression, death, the initiation of subsequent anticancer therapy, or patient's withdrawal of consent, whichever occurs first. CT/MRI scans will be collected for sensitivity analysis by blinded independent central review (BICR).

Patients who discontinue MIRV for reasons other than progressive disease (PD) will continue with tumor assessments until documentation of PD or the start of new anticancer therapy, whichever comes first.

All patients who discontinue MIRV will be followed for survival every 3 months (± 1 month) until death, lost to follow-up, withdrawal of consent for survival follow-up, or End of Study (EOS), whichever comes first.

2.2.1. Study Population

All patients must have confirmed diagnosis of high-grade serous EOC, primary peritoneal cancer, or fallopian tube cancer. Patients must also have the following:

- Patients must have at least 1 lesion that meets the definition of measurable disease by RECIST v1.1 (radiologically measured by the Investigator).
- Patients must have received at least 1 but no more than 3 prior systemic lines of anticancer therapy, including at least 1 line of therapy containing bevacizumab, and for whom single-agent therapy is appropriate as the next line of treatment.
- Patient's tumor must be positive for FRα expression as defined by the Ventana FOLR1 (FOLR-2.1) CDx assay.

See Protocol IMGN853-0417, Section 3.1 for a complete list of the inclusion/exclusion criteria.

2.2.2. Power and Sample Size

The primary endpoint of this study is ORR as assessed by the investigator. The study is designed to test the null hypothesis that the ORR is 12% (Eisenhauer 2009, Pujade-Lauraine 2014). The ORR will be estimated using the efficacy evaluable population as defined in Section 3.12.3.

Approximately 110 patients will be enrolled so that a total of 105 patients will be efficacy evaluable. A sample size of 105 efficacy evaluable patients achieves 90% power to detect a difference in ORR of 12% (24% vs 12%) using a one-sided binomial test. The target significance level (one-sided α level) is 0.025. The actual significance level achieved by this test is 0.0242. These results assume that the ORR is 12% under the null hypothesis and 24% under the alternative hypothesis.

2.2.3. Treatment Randomization and Blinding

Randomization and blinding are not applicable in this single-arm, open-label study.

2.2.4. Assessment Schedule

See Protocol IMGN853-0417, Table 2 for study schedule of assessments.

2.3. Interventions

2.3.1. Clinical Trial Material

MIRV will be administered at 6 mg/kg AIBW as an IV infusion following preparation as outlined in the Pharmacy Manual on day 1 of every 3-week cycle.

The protocol provides additional details in Protocol IMGN853-0417, Section 5.4.

3. GENERAL ANALYTICAL CONSIDERATIONS

3.1. Data Sources

Data will be captured using validated, electronic data capture (EDC) systems. Data will be documented in various source documents (eg, the patient medical chart) and then manually entered into the clinical trial database. Protocol IMGN853-0417, Section 11 provides additional details regarding data recording and handling.

3.2. Definition of Baseline

Study Day 1 (ie, Cycle 1 Day 1) will be designated as the first day a patient receives MIRV. The baseline value is defined as the last non-missing value on or before the date of first dose of MIRV.

3.3. Missing Data

Partial dates are allowed in the clinical database for subsequent anti-cancer therapy start date, adverse event (AE) onset and resolution dates, concomitant medication start and stop dates, and concomitant procedure dates. An entry for the year is required in the clinical database for each of these dates. Only the month and day may be entered as unknown. Prior anticancer systemic therapy start and stop dates and subsequent anticancer therapy stop date allows for unknown dates in the clinical database. Dates from these forms will be reported in listings as collected. Every effort will be made to query missing dates.

For records with missing AE onset date, the following procedure will be employed for use in determining whether the AE is treatment emergent:

• AE onset dates with missing day and non-missing month will be assumed to occur on the first day of the non-missing month, except for AEs occurring in the first month of dosing, in which case the date will be the first day of dosing.

• AE onset dates with missing month will be assumed to occur on the first day of the non-missing year (ie, January 1), except for AEs occurring in the first year of dosing, in which case the date will be the first day of dosing.

For records with a missing medication start and/or stop date, the following procedure will be employed for use in determining whether the medication is prior or concomitant:

- Medication start dates with a missing day and non-missing month will be assumed to occur on the first day of the non-missing month, except for medications occurring in the first month of dosing, in which case the date will be the first day of dosing.
- Medication start dates with missing month will be assumed to occur on the first day of the non-missing year (ie, January 1), except for medications occurring in the first year of dosing, in which case the date will be the first day of dosing.
- Medications that are not ongoing and have a medication stop date with a missing day and non-missing month will be assumed to occur on the last day of the non-missing month.
- Medications that are not ongoing and have a medication stop date with a missing month will be assumed to occur on the last day of the non-missing year (ie, December 31).

For records with a missing procedure date, the following procedure will be employed for use in determining whether the procedure is prior or concomitant:

- Procedure dates with a missing day and non-missing month will be assumed to occur on the first day of the non-missing month, except for procedures occurring in the first month of dosing, in which case the date will be the first day of dosing.
- Procedure dates with missing month will be assumed to occur on the first day of the non-missing year (ie, January 1), except for procedures occurring in the first year of dosing, in which case the date will be the first day of dosing.

For records with a missing prior anti-cancer systemic therapy start and/or stop date, and/or disease progression date from prior therapy, the following procedure will be employed for use in calculating the platinum-free interval (PFI):

- If the stop date of prior platinum therapy is completely missing OR only the year is available, the PFI will be set as missing.
- If both year and month of stop date of prior platinum therapy are available and only day is missing, the stop date will be imputed by the first day of the month.
- If the disease progression date from prior platinum therapy is completely missing OR only the year is available, the PFI will be set as missing.
- If both year and month of disease progression date from prior platinum therapy are available and only day is missing, the date of disease progression will be imputed by the last day of the month.

For records with a missing subsequent anti-cancer therapy start date, the following procedure will be employed for use in deriving efficacy variables such as PFS and BOR.

• The start date of subsequent anti-cancer therapy will be imputed by the earliest possible date that is not contradicting with any other available data in the database.

For records with a partial death date, the following procedure will be employed for use in deriving time to event variables (PFS, OS, DOR).

• The death date will be imputed by the earliest possible date that is not contradicting with any other available data in the database.

All other data will be reported as they are collected. No imputation methods will be used to replace missing data unless otherwise stated in this document.

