8. ASSESSMENT OF SAFETY

8.1. Recording Adverse Events and Serious Adverse Events

Adverse Events (AEs), including those attributed to study procedures, will be documented in the clinical trial database and monitored continuously throughout the study from the time of informed consent until 30 days after the patient's last study treatment.

Only AEs/SAEs which are considered related to a study procedure (ie blood draw or fresh tumor biopsy) will be captured during the pre-screening period, ie from the time of signing of the pre-screening informed consent (if one is utilized) until the time of signing of the main study informed consent, or until the patient is determined to be a screen failure. All AEs and SAEs, regardless of causality, will be captured after the main study ICF has been signed.

SAEs will continue to be followed by ImmunoGen Pharmacovigilance until resolution, stabilization or return to baseline. Beyond this defined reporting period, any unsolicited SAE assessed as related to the study drug by the Investigator and reported to ImmunoGen will be collected and processed. Additional information obtained after database lock, will reside solely in the safety database.

The Investigator should follow and provide updates for all AEs until clinical recovery is complete, laboratory values return to normal, the patient stabilizes, or death occurs, to ensure the safety of the patients. This may mean that observations continue beyond the last planned visit per protocol and that additional investigations may be requested by the Sponsor.

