6.2. AEs

AEs will be documented on the AE CRF and monitored continuously throughout the study from the time of informed consent until 30 days after the patient's last MIRV or until the event has resolved, stabilized, or returned to baseline. AEs attributed to study procedures, including those events that occur prior to the first dose, should also be documented on the AE CRF.

AE data are available to ImmunoGen from 2 sources, the clinical database and the serious adverse event (SAE) forms. While reconciliation will be performed, the production of data summaries and listings will be based on the data collected on the clinical database.

Pre-treatment AEs are defined as AEs with an onset date prior to the first dose of MIRV. TEAEs are defined as AEs with an onset date on or after the first dose of MIRV, and within 30 days of the last dose of MIRV or prior to the start of a new anti-cancer treatment, whichever occurs first. Medical history conditions that exist before the initiation of MIRV but worsen in severity during the study will also be recorded on the AE CRF as an AE and will be included as treatment-emergent in the summary tables and listings.

The adverse events will be coded using MedDRA (Version 24.0), associating lower-level terms with PT and SOC by the primary hierarchy. The tables will display the counts and percentages of patients who reported at least 1 TEAE in each SOC represented in the AE data. Within each SOC, the tables will display the counts and percentages of patients reporting at least 1 TEAE as designated by the PT.

AEs are graded using CTCAE Version 5.0. AE summaries may include summaries for all AEs and by the maximum CTCAE grade for the item being summarized (ie, SOC or PT). In these cases, the outputs will include a row for All Grades as well as rows for the 5 potential CTCAE grades, Grade 1 (Mild), Grade 2 (Moderate), Grade 3 (Severe), Grade 4 (Life threatening or disabling), or Grade 5 (Death). AEs missing a severity grade will not be included in the Grade 1-5 rows of the tables. An AE reported by a patient more than once will be represented in the most severe category. TEAEs will be categorized as MIRV-related if "Possibly Related", "Probably

Related", or "Definitely Related" is selected by investigator. AEs missing relationship to MIRV will be included in the Related TEAE tables and listings.

The following summary tables will be produced:

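### SAP 3.3 imputes a partial AE onset to the first-dose day without checking the resolution date, so an event known to have ended before dosing could be counted as treatment-emergent

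*SAP*

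**What the plan says.** SAP 3.3 (Missing Data) allows partial dates for "adverse event (AE) onset and resolution dates", with the year always required. It gives the purpose of the AE rule: "For records with missing AE onset date, the following procedure will be employed for use in determining whether the AE is treatment emergent". Two bullets follow.

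- Day missing, month known: the first of that month, "except for AEs occurring in the first month of dosing, in which case the date will be the first day of dosing".
- Month missing, year known: 1 January of that year, "except for AEs occurring in the first year of dosing, in which case the date will be the first day of dosing".

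Neither bullet mentions the resolution date.

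SAP 6.2 then classifies on onset. "Pre-treatment AEs are defined as AEs with an onset date prior to the first dose of MIRV", and "TEAEs are defined as AEs with an onset date on or after the first dose of MIRV", up to 30 days after the last dose or the start of a new anticancer treatment. The end date plays no part in either definition.

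Events can be on file before dosing. Protocol 8.1 states: "All AEs and SAEs, regardless of causality, will be captured after the main study ICF has been signed". Before that consent, only procedure-related events are collected. Footnote a of the protocol's schedule of assessments (Table 2) places main consent within 28 days before C1D1.

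For two other kinds of date, the start of subsequent anticancer therapy and death, SAP 3.3 requires the value to be "imputed by the earliest possible date that is not contradicting with any other available data in the database".

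**The concern.** Moving an uncertain onset to the first-dose day is a sensible conservative convention: if the event might have begun on treatment, count it as if it did. That reasoning does not apply when the recorded resolution date is earlier than the first dose. The timing relative to treatment is then known, and the rule overrides it with an impossible sequence in which onset follows resolution.

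Because SAP 6.2 uses onset alone, nothing downstream corrects this. The event would enter the TEAE tables and, where its grade or seriousness qualifies, the Grade 3 or higher or serious TEAE tables. It would also leave the pre-treatment AE listing. What is at stake is the accuracy of individual rows, mainly for uncommon terms where one patient is visible.

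**Working it through.** The plan states no figure on this point, so there is none to reproduce. The check applies the written rule to test records.

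**Inputs.** The two AE bullets of SAP 3.3 and the onset-only definitions of SAP 6.2. The first dose is assumed to be 20 March 2021. The first month of dosing, which the SAP does not define, is read as the calendar month of the first dose. With the day unknown, that is the workable reading.

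| Recorded onset | Recorded end | Onset under SAP 3.3 | Class under SAP 6.2 | Class with an end-date check |
|---|---|---|---|---|
| March 2021, day missing | 10 March 2021 | 20 March, 10 days after its end | TEAE | Pre-treatment |
| 2021, month missing | 28 February 2021 | 20 March, 20 days after its end | TEAE | Pre-treatment |
| March 2021, day missing | 25 March 2021 | 20 March | TEAE | TEAE |
| March 2021, day missing | Ongoing | 20 March | TEAE | TEAE |
| February 2021, day missing | 25 February 2021 | 1 February | Pre-treatment | Pre-treatment |

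Only the first two records change. Both are known to have ended before any drug was given. The conservative handling of the third and fourth is preserved.

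**How much of screening the rule reaches.** Assume a 28-day window before first dose and first-dose days spread evenly over 2020 and 2021 (731 days), giving 28 × 731 = 20,468 screening days.

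- Same calendar month as first dose: for a first dose on day d of the month, min(d − 1, 28) of the 28 preceding days qualify. The sums are 462 for a 31-day month, 434 for 30 days, 406 for 29 and 378 for 28. The total is 14 × 462 + 8 × 434 + 406 + 378 = 10,724, and 10,724 / 20,468 = 52%.
- Same calendar year: each January loses 28 + 27 + … + 1 = 406 days. So 1 − 812 / 20,468 = 96%.

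These are shares of screening days that fall under each bullet. They are not rates of misclassified events, which also need a partial onset that survives query and an end before first dose.

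**Effect per case.** With about 110 treated patients, one misclassified patient adds 1/110 = 0.9 percentage points to a TEAE row. This is a maximum. SAP 6.2 counts patients with at least one TEAE per row, so a patient already counted there adds 0.

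**Comparison with medications.** SAP 3.3 imputes partial medication start dates in the same way, but SAP 6.6 defines a prior medication by a stop date before the first dose. The end date therefore settles the class. AEs have no such backstop.

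**The case against.** The strongest reply is that the effect may never occur. It needs, in one record, an AE between consent and dosing, an onset still partial after query, an onset in the month or year of first dose, and a recorded end before dosing. SAP 3.3 commits to querying missing dates. For general AEs the window is at most about four weeks, and an unknown onset month in so short a window is improbable. All of this stands, and it limits the size. It does not change what the rule does to the records that remain.

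Other mitigations also stand. SAP 3.3 has dates listed as collected, and the all-AE listing in SAP 6.2 shows onset and end dates, so a careful reader could spot the sequence. AEs within 7 days of a fresh biopsy have their own summary whether or not they are TEAEs (SAP 6.2.1). Serious events are reported within 24 hours of the investigator learning of them (Protocol 8.2.1) and reconciled with the clinical database (SAP 6.2), so an unresolved partial onset is less likely there.

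The consistency condition used for therapy and death dates belongs to an earliest-possible-date rule for efficacy variables. It is not the same rule as the one proposed here. It shows only that the SAP consults other data when imputing some dates.

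It might be said that a programmer would check the end date anyway. SAP 1.1 makes the SAP govern the analysis and requires deviations to be documented, so such a check would be a departure from the plan as written.

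**Conclusion.** The gap is real and minor. As written, an AE known to have resolved before first dose could be given an onset after its own end and be counted as a TEAE. The documents give no count of such records, and the number is probably small. Each adds at most 0.9 points to a row, assuming about 110 treated patients, and may add nothing. The direction is over-counting of TEAEs. Objective response rate, duration of response, progression-free survival and overall survival are not affected.

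A reader might infer more than the documents support.

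- The missing-month bullet might seem to expose many months of pre-dose events. It does not: general capture begins at main consent, and earlier events are recorded only if procedure-related.
- The safety tables might be thought materially inflated. Nothing in the documents indicates how many partial onsets will remain, so no expected count can be given.
- Imputing to the first-dose day might be thought wrong in general. It is reasonable whenever the resolution date is missing, ongoing, or on or after first dose. The defect is only the missing end-date check.

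The conclusion rests on the calendar-month reading of the first month of dosing.

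**What to change.** Add to both AE bullets in SAP 3.3: *unless the AE resolution date (complete, or partial but in a month or year earlier than that of first dose) shows that the event ended before first dose, in which case the AE is classed as pre-treatment.* AEs with a partial onset in the month or year of first dose whose resolution date is missing, ongoing, or on or after first dose stay treatment-emergent, as now. It would also help to state that the first month and first year of dosing mean the calendar month and year of the first dose.

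The cost is one clause and one programming condition. SAP 1.1 permits changes before final database lock. No genuinely uncertain onset loses treatment-emergent status.

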3. STUDY POPULATION

3.1. Criteria for Selection of Patient Population

3.1.1. Inclusion Criteria

1. Female patients ≥ 18 years of age
2. Patients must have a confirmed diagnosis of high-grade serous EOC, primary peritoneal cancer, or fallopian tube cancer

3. Patients must have platinum-resistant disease:
 - a. Patients who have only had 1 line of platinum based therapy must have received at least 4 cycles of platinum, must have had a response (CR or PR) and then progressed between > 3 months and ≤ 6 months after the date of the last dose of platinum
 - b. Patients who have received 2 or 3 lines of platinum therapy must have progressed on or within 6 months after the date of the last dose of platinum
Note: Progression should be calculated from the date of the last administered dose of platinum therapy to the date of the radiographic imaging showing progression
Note: Patients who are platinum-refractory during front-line treatment are excluded (see exclusion criteria)
4. Patients must have progressed radiographically on or after their most recent line of anticancer therapy
5. Patients must be willing to provide an archival tumor tissue block or slides, or undergo procedure to obtain a new biopsy using a low-risk, medically routine procedure for immunohistochemistry (IHC) confirmation of FR α positivity
6. Patient's tumor must be positive for FR α expression as defined by the Ventana FOLRI Assay
7. Patients must have at least 1 lesion that meets the definition of measurable disease by RECIST v1.1 (radiologically measured by the Investigator)
8. Patients must have received at least 1 but no more than 3 prior systemic lines of anticancer therapy, including at least 1 line of therapy containing bevacizumab, and for whom single-agent therapy is appropriate as the next line of treatment:
 - a. Adjuvant \pm neoadjuvant considered 1 line of therapy
 - b. Maintenance therapy (eg, bevacizumab, PARP inhibitors) will be considered part of the preceding line of therapy (ie, not counted independently)
 - c. Therapy changed due to toxicity in the absence of progression will be considered part of the same line (ie, not counted independently)
 - d. Hormonal therapy will be counted as a separate line of therapy unless it was given as maintenance
9. Patients must have an Eastern Cooperative Oncology Group Performance Status (ECOG PS) of 0 or 1
10. Patients must have completed prior therapy within the specified times below:

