4.1.4. Disease Characteristics, Prior Therapy, and Gene Mutations

Listings of all collected data related to disease characteristics and prior therapy will be provided. A summary of the following elements will also be provided:

- ECOG performance status (0/1)
- Primary diagnosis (epithelial ovarian cancer, fallopian tube cancer, primary peritoneal cancer, other)
- Histology

- Disease stage at initial diagnosis
- Histologic grade
- Prior radiotherapy (yes/no)
- Prior systemic therapy
 - The number of prior systemic therapies is defined as the number of distinct treatment regimens.
- Prior cancer related surgery (yes/no)
- Prior exposure to doxorubicin (yes/no), topotecan (yes/no), taxanes (yes/no)
- Prior exposure to PARP inhibitors (yes/no/uncertain)
 - If patient participated in a double-blind randomized trial comparing PARP inhibitor to placebo and the actual treatment was unknown, patient will be summarized under 'uncertain' category.
- Any *BRCA* mutations (yes [*BRCA1*, *BRCA2*]/no)
- Primary platinum-free interval (months, ≤ 12 months vs > 12 months)
 - Defined as time from last dose of 1st line platinum therapy to the date of disease progression and/or relapse following 1st line therapy.
- Platinum-free interval (months, ≤ 3 months vs $\geq 3-6$ months, vs ≥ 6 months)
 - Defined as time from last dose of latest line platinum therapy to the date of disease progression and/or relapse following that line of therapy.

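### When a day is missing, the SAP's rule gives the longest possible platinum-free interval, so the baseline table can show some eligible patients above 6 months

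*SAP*

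**What the plan says.** SAP 3.3 (Missing Data) gives a separate imputation rule for the PFI:

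- Platinum stop date: when "only day is missing, the stop date will be imputed by the first day of the month".
- Progression date: when "only day is missing, the date of disease progression will be imputed by the last day of the month".
- If either date lacks its month as well, or is absent altogether: if it "is completely missing OR only the year is available, the PFI will be set as missing".

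SAP 4.1.4 then gives the interval itself: "Defined as time from last dose of latest line platinum therapy to the date of disease progression and/or relapse following that line of therapy". It is summarised at baseline with cuts at 3 and 6 months. A primary PFI, after first-line platinum, is cut at 12 months.

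Protocol 3.1.1 sets the entry limit. Patients with two or three platinum lines "must have progressed on or within 6 months after the date of the last dose of platinum". Those with one line must have progressed after more than 3 and up to 6 months. A note says how to measure this: "Progression should be calculated from the date of the last administered dose of platinum therapy to the date of the radiographic imaging showing progression".

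**The concern.** PFI is the progression date minus the stop date. The rule takes the earliest possible start and the latest possible end, so it returns the longest interval that the recorded months allow. The two errors add and cannot cancel. The SAP gives no reason for this choice.

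The 6-month cut in the table is also the eligibility limit for platinum resistance. This is a single-arm trial tested against a fixed 12% ORR, so readers use the baseline table to judge whether the patients resemble the setting behind that 12%. An eligible patient shown above 6 months looks either like an entry violation, which SAP 4.2.3 reports as a major deviation category, or like a more platinum-sensitive patient. Either impression would come from the imputation.

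The same section requires imputed death and subsequent-therapy dates to be consistent with other data. The PFI rule has no such bound.

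**Working it through.** The documents give no figure for the effect of this rule, so there is none to reproduce.

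**Inputs.** From SAP 3.3: stop day becomes the 1st, progression day becomes the last of the month. From protocol 3.1.1: true PFI up to 6 months. Assumptions: stop dates spread evenly over a 4-year calendar cycle (1,461 days); true PFI uniform over 0-6 or 3-6 months, in whole days up to 182; top category read as above 6 months. No day-to-month conversion is stated, so I used limits of 182.6 days (6 × 30.4375), 183 and 184.

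**Example.** Stop 20 March, progression 5 September: the true PFI is 169 days (169/30.4375 = 5.6 months). With both days missing, the rule uses 1 March to 30 September, 213 days (7.0 months). Day 15 for both gives 184 days, which is closer but still above two of the three limits.

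**Average error.**

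- Setting the stop to the 1st adds (day of month − 1). A month of n days contributes n(n−1)/2. Over four years: 28 × 465 + 16 × 435 + 3 × 378 + 1 × 406 = 21,520 days, and 21,520/1,461 = 14.7 days.
- Setting progression to the last of the month adds (n − day), with the same mean by symmetry.
- Both missing: 2 × 14.73 = 29.5 days, maximum 30 + 30 = 60.
- The error is never negative. It is zero in 3.3% of cases with one day missing and 0.1% with both.

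**Share moved above 6 months, among patients with a partial date** (all stop dates and true PFIs enumerated):

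| True PFI (assumed) | Limit | One day missing, SAP rule | Both missing, SAP rule | Both missing, day 15 |
|---|---|---|---|---|
| 0-6 months | >182.6 d | 8.0% | 14.0% | 4.3% |
| 0-6 months | >183 d | 7.5% | 8.3% | 2.6% |
| 0-6 months | >184 d | 7.0% | 8.3% | 0% |
| 3-6 months | >182.6 d | 16.2% | 28.1% | 8.6% |
| 3-6 months | >183 d | 15.1% | 16.6% | 5.2% |
| 3-6 months | >184 d | 14.1% | 16.6% | 0% |

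**Who can cross** (182.6-day limit). With one day missing, nobody with a true PFI below 153 days crosses; 49% of those at 5-6 months do. With both missing, nobody below 123 days crosses; 16.5% at 4-5 months and 68% at 5-6 months do.

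**The 3-month cut.** Of patients with a true PFI of 2-3 months and a partial date, 48% (one missing) or 50% (both) move above 3 months.

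**Patients affected.** If 5-20% of 105 had a partial date (assumption) and true PFI were uniform over 0-6 months: 5.25 × 0.080 = 0.4 to 21 × 0.140 = 2.9. If every true PFI lay in 3-6 months, the range would be 5.25 × 0.162 = 0.9 to 21 × 0.281 = 5.9.

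**The case against.** The strongest objection is that nothing inferential depends on this. Eligibility is judged at Screening (protocol 7.2) from the last administered dose and the imaging date, not from the SAP's imputed PFI. PFI does not define an analysis population (SAP 3.12), is not a subgroup (SAP 5.4) and is not a covariate (SAP 3.6). All of that stands. A reader might infer that the rule changes who is in the trial or biases the ORR. The documents do not support either inference.

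A reader might also infer that the rule always lengthens PFI, or that 28% of the trial would be misclassified. Neither follows. Complete dates are untouched, and a date without its month gives a missing PFI. The 28% applies only to patients with both days missing, under a 3-6 month range and a 182.6-day limit. The 3-month floor is an entry requirement only for patients with one platinum line; over 0-6 months the figure is 8-14%.

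SAP 3.3 also promises to query missing dates and to list them as collected. That should reduce the number of partial dates and keep them visible, but it does not correct the rule for those that remain.

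Finally, mid-month imputation has a cost. Unbounded, with one day missing, it gives a negative interval in 11-14% of cases with a true PFI under 31 days, which the first/last rule never does. That is why the fix needs a bound.

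**Conclusion.** The point holds as a minor reporting issue. When a day is missing, the written rule never shortens PFI and nearly always lengthens it. It can move patients with a true PFI of about 4-5 months or more above the 6-month cut, and about half of those at 2-3 months above the 3-month cut. The direction of the bias follows from the text alone. The shares rest on an assumed uniform PFI and an unstated month conversion, and the patient count rests on an assumed 5-20% frequency of partial dates. Only the baseline PFI summary is affected. It still merits correction, because it describes how platinum-resistant the population of a single-arm trial is, and its bias has a known sign.

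**What to change.** In SAP 3.3, replace the two day-missing bullets. Impute day 15 for either date, bounded so that the result does not contradict other recorded dates: stop no later than progression, and progression no later than the first MIRV dose. State the day-to-month conversion in SAP 4.1.4, and footnote the PFI rows with the number of imputed values.

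The cost is two revised bullets, one added sentence and one footnote, with no change to any efficacy analysis. The bounding rule adds a little programming. Some misclassification remains: with both days missing, about 0-9% of such patients would still be classed above 6 months, against 8-28% under the present rule.
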